To assess target engagement for the PO intervention (CIT), we will use two tasks. The first is the original contour integration test recommended by the CNTRICS initiative for use in treatment studies of schizophrenia, namely the Jittered Orientation Visual Integration (JOVI) task. The JOVI involves identifying the direction of an egg-shaped contour made up of individual Gabor elements with gaps between them so that the participant has to perceptually integrate the Gabors to perceive the egg (see Fig. 3). The task has been optimized for use in clinical trials (see D.6.b). Although there are differences between the PO training task (CIT) and the JOVI in terms of the specific stimuli (i.e., circular vs. oval shapes, respectively) and response requirements (identifying the location of the target circle vs. indicating whether the centrallypresented egg-shaped contour is pointing left or right), which should preclude confounds based on low-level perceptual learning (e.g., learning that is specific to one area of visual space, or to a single shape), we will also include a second outcome measure, one that does not share method variance with the training task. The second PO task uses the Ebbinghaus illusion, in which a center circle appears smaller if it is surrounded by (i.e., grouped with) larger circles and appears larger if it is surrounded by smaller circles (see Fig. 5). The task requires subjects to choose which display (on the left or right of the screen) contains the array with the larger central circle. By manipulating the difference between the actual sizes of the central circles, and whether the size of the surrounding circles causes the inner target circle to appear smaller or larger than its actual size, a psychophysically precise measure of illusion strength is obtained. [name] has used this task extensively, and one of its appealing aspects is that, due to their reduced grouping of the central target and the surrounding circles, people with schizophrenia perform more accurately (in all studies cited above) than controls on trials in which surrounding context is normally misleading (e.g., when the larger of the two inner circles is made to appear smaller by surrounding it with large circles). Evidence that both the JOVI and Ebbinghaus tasks involve PO comes from a significant *inverse* correlation between scores such that a lower score on the JOVI is associated with higher scores in the misleading condition on the Ebbinghaus task.

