Clear and refutable hypotheses of the R61 are: H1a) UE or UE&CIT will lead to significantly greater gains in CS than will ACCT and/or H1b) CIT or UE&CIT will produce significantly greater improvements in PO compared to ACCT. The **Go Signal** for continuing to the R33 will be a differential improvement, with an effect size of at least d=0.4, favoring UE or UE&CIT compared to ACCT on the psychophysical and/or electrophysiological CS task, *and/or* CIT or UE&CIT compared to ACCT on the JOVI and/or Ebbinghaus task. If a "go" signal is obtained, results of the R61 will be used to identify the most effective and efficient treatment (UE, CIT, or UE&CIT), and duration/dose, for use in the R33.

**Clear and refutable hypotheses of the R33 are:** H1) The optimal treatment identified in the R61 (e.g., UE&CIT) will be more effective than the control treatment (ACCT) in improving CS or PO in a new and larger sample; and H2) Improvements in target function will be related to changes on visual cognitive (i.e., visual learning and memory, reading), social cognitive (i.e., facial emotion recognition) and functional capacity measures. If the hypotheses in the R33 are confirmed, the results will inform the design of a later RCT to assess the efficacy of a visual remediation treatment for schizophrenia on a wider range of outcome variables. Instructions for the R33 state that it "should not be powered as strong tests of clinical efficacy but rather should test the link between... target engagement and functional outcome." Therefore, while we expect the correlations for R33 Aim 2 to be statistically significant, we do not hypothesize what the effect sizes will be. However, we would power a subsequent study based on the observed effect sizes in the R33.

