Milestones (Go/No-Go Criterion): We will proceed to the R33 phase if: 1) the UE-related effect size (i.e., the effect size of the difference between the UE&ACCT (or UE&CIT) and ACCT&ACCT groups in the degree of change in CS) is greater than or equal to Cohen's d=0.4 for **either** the psychophysical **or** ssVEP CS task: and/or 2) the CIT-related effect size (i.e., the effect size of the difference between CIT&ACCT (or UE&CIT) and ACCT&ACCT groups in the change on **either** of the PO tasks) is greater than or equal to d=0.4. Pre-post change scores for CS and PO target assessments will be calculated for each individual and used to determine effect sizes between groups. We will not control for baseline values consistent with recommendations to use "straight" change scores when examining cognitive change across two time points.

Rationale for our effect size choice: The effect size criterion we have chosen for the R61 "go" signal (d=0.4)

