circles are presented by themselves (i.e., the no-context condition). On the other half, the targets are surrounded by larger or smaller circles that either *facilitate* perceiving the true size difference of the target circles (helpful condition: the larger inner circle is surrounded by smaller circles, making it appear larger than its actual size, and the smaller inner circle is surrounded by larger circles, making it appear smaller than its actual size, and these effects combine to amplify the real size difference between the target circles: see Fig. 5. where the target circle on the right is 2% larger in each of the 3 panels), or hinder perceiving the true size difference (misleading condition: the larger inner circle is surrounded by larger circles, making it appear smaller than its actual size, and the smaller inner circle is surrounded by smaller circles, making it appear larger than its actual size). Stimuli remain on the screen until the subject responds or for 2 seconds (whichever occurs first). If a response is not recorded within 2 seconds, the trial is recorded as a guess (0.5 correct). Trials are separated by 200 msec. The two target circles always differ in actual size and this size difference varies in magnitude across trials. The order of trial types is randomized for each subject, as is the side on which the larger inner circle appears on each trial. In total, the task contains 192 trials, and typically takes 7 minutes. The key metric from this task is the difference between the helpful and

misleading conditions, controlling for no-context performance, or: [(Helpful – no context) – (misleading – no context)]. Reduced grouping is reflected in scores closer to 0.

Visual Acuity: While not a target for this study, acuity will be assessed to determine whether it moderates the effects of UE and/or CIT. We will use ETDRS charts, which are the "gold standard" for acuity testing. **D.6.c Other Outcome Measures for R33** 

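### The Ebbinghaus key metric does not control for no-context performance: the term cancels, so 96 of the 192 trials carry no weight in a score that can give a go by itself

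*Combined protocol and SAP*

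**What the plan says.** All references are to the combined protocol and SAP.

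- **The task (D.6.b, Ebbinghaus Illusion Task).** There are 192 trials. On half of them the two target circles appear alone, which is the no-context condition. On the rest, surrounding circles either help or mislead. The actual size difference is never zero, and "this size difference varies in magnitude across trials". On time-outs: "If a response is not recorded within 2 seconds, the trial is recorded as a guess (0.5 correct", bracket then closed.
- **The score (same place).** The key metric is the difference between the helpful and misleading conditions, "controlling for no-context performance, or: [(Helpful – no context) – (misleading – no context", followed by the closing brackets. Values nearer 0 mean weaker grouping.
- **Its purpose (B. Significance).** The task was added as a second measure of perceptual organization, "one that does not share method variance with the training task". The section says that "a psychophysically precise measure of illusion strength is obtained".
- **The go rule.** Section B allows a go for "CIT or UE&CIT compared to ACCT on the JOVI and/or Ebbinghaus task". D.3 (Milestones) is met when the effect on either "of the PO tasks) is greater than or equal to d=0.4". D.3 also fixes the quantity analysed: "Pre-post change scores for CS and PO target assessments will be calculated for each individual and used to determine effect sizes between groups". There is no baseline adjustment.

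**The concern.** The plan states a property that its own formula does not have. A reader would take it that 96 trials without context guard the score against general changes in performance, such as better attention, faster responding or finer size discrimination. They do not enter it.

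This matters because of the role the score plays. It can trigger the go without support from the JOVI, and it feeds the choice of treatment for the R33. The JOVI has its own protection in D.6.b: catch trials, with 75% accuracy required for inclusion. No such rule is stated for the Ebbinghaus task. Subtraction of no-context performance is the only guard named there, and it has no effect.

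**Working it through.** **1. The plan's formula.** Write H, M and N for helpful, misleading and no-context performance.

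(H - N) - (M - N) = H - N - M + N = H - M

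Take H = 0.921, M = 0.500, N = 0.760: (0.161) - (-0.260) = 0.421. Change N to 0.887: (0.034) - (-0.387) = 0.421. The score does not depend on N. Over 100,000 random triples, the largest difference between the formula and H - M was 0.

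**2. Trials with no weight.** 0.5 × 192 = 96. The other 96 carry the whole score.

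**3. Does a later step restore the control?** The go effect size is computed from change scores in D.3. The further R61 models there adjust for antipsychotic dose and type and anticholinergic load, and look at baseline moderators. The R33 model in D.4 has group, time, their interaction and unspecified moderators or mediators, with age as the example. None names no-context performance.

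**4. What H - M removes and what it leaves.** A shift that adds equally to H and M cancels. Lapses do not. If a proportion L of trials is answered at random or timed out at 0.5,

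accuracy = (1 - L) × Φ(x/s) + L/2,

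where x is the size difference plus the illusion bias (helpful) or minus it (misleading), and s is the noise SD. The L/2 terms cancel in H - M, which leaves (1 - L) times the lapse-free difference. Fewer lapses therefore raise the score with the illusion unchanged, and D.6.b would read that as stronger grouping.

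**5. Illustrative size.** The plan gives no size range, lapse rate or SD of change. These are assumptions: size differences 0.5 to 3 in steps of 0.5 noise SDs, bias = s = 1, SD of change 0.12 to 0.20.

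- Lapse-free H - M = 0.984 - 0.709 = 0.275.
- L = 0.20: 0.80 × 0.275 = 0.220. L = 0.15: 0.234. L = 0.10: 0.248.

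| Lapses, trained arm | Lapses, control arm | Net shift | d (SD 0.20 to 0.12) |
|---|---|---|---|
| 20% to 10% | unchanged | 0.0275 | 0.14 to 0.23 |
| 20% to 10% | 20% to 15% | 0.0138 | 0.07 to 0.11 |
| 20% to 10% | 20% to 10% | 0 | 0 |

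**6. Chance that one comparison shows d of at least 0.4.** With 20 per arm, the cut-off on the t scale is 0.4 × √(20/2) = 1.265, with 38 df and noncentrality d × √10. At d = 0 the chance is 10.7%; at 0.138 it is 20.8%; at 0.229 it is 29.9%. For the second row of the table it is about 15% to 19%.

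**7. Direction if noise changes.** Both cases use varying size differences.

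- Assumptions of step 5 with L = 0.10, s halved: H - M falls from 0.248 to 0.228.
- Size differences 2% to 10%, illusion fixed at 6%, noise 8% to 4%, no lapses: H - M rises from 0.421 to 0.494.

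**8. Would the unused trials show a lapse change?** Under step 5, lapse-free no-context accuracy is 0.906. With L = 0.20 it is 0.80 × 0.906 + 0.10 = 0.825. With L = 0.10 it is 0.90 × 0.906 + 0.05 = 0.865. The same lapse change moves no-context accuracy by about 0.04, so reporting it by arm is informative.

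**The case against.** The strongest reply is that only a phrase is wrong. D.6.b itself calls the metric the helpful-misleading difference, which is what the formula gives. No figure in the plan changes, and H - M is a reasonable within-person contrast. This stands as far as it goes. It does not rescue the claimed control, on a score that can decide the go.

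A second reply is that the size of any bias rests on assumptions. That also stands. Nothing in the documents suggests that lapses would fall in one arm only. D.5 says the control programme targets attention and memory. The control arm receives it throughout, and the CIT&ACCT arm receives it too.

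A third reply is that separate no-context scores, matched to each context condition, need not cancel. That is true, but the plan describes one no-context condition and one term.

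Three stronger readings are tempting, and the documents do not support them:

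- *A reader might infer that the score is biased towards a false go.* Direction depends on what changes: step 7 gives movement both ways, and equal change in both arms gives none.
- *A reader might model the task with one fixed size difference and obtain a larger artefact.* The plan excludes that, since the size difference varies across trials.
- *A reader might conclude that a go should require an effect adjusted for no-context change.* That adjustment conditions on a post-randomisation variable and works only partly. In simulation (20 per arm; 96, 48 and 48 trials) it reduced the lapse artefact for sizes 0.5 to 3 from 0.0251 to 0.0205, or 18%, and by 3% to 44% across the settings tried. With noise halved it enlarged the bias for those sizes from -0.014 to -0.020.

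The plan also treats the R33 as a replication. With 50 per arm, a two-group t-test approximation gives favourable significance about 10% to 20% of the time at d of 0.14 to 0.23. The exposure is therefore mainly the R61 go and the choice of treatment.

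**Conclusion.** The point holds in this form. The cancellation and the zero weight are exact, given one no-context score per person and visit. The count of 96 takes half the trials to mean half of 192. That the Ebbinghaus task alone can give a go follows directly from section B and D.3.

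The consequence is not established in size or direction. H - M remains usable and removes additive shifts common to both conditions. It is not illusion strength alone, because lapses, time-outs scored 0.5 and discrimination noise can move it. Bias in the go comparison needs a between-arm difference in one of these. On the assumed values, one-sided lapse reduction gives d of 0.14 to 0.23, well short of the 0.4 threshold but enough to raise the chance of crossing it from 11% to between 21% and 30%. If control lapses fall half as far, d is 0.07 to 0.11.

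This should be corrected before the go/no-go analysis. It is not a reason to discard the task.

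**What to change.** 1. In D.6.b, state the score as Helpful - misleading and delete the claim that it controls for no-context performance.
2. Before the go/no-go analysis, prespecify that any Ebbinghaus go is reported with no-context accuracy and time-out rates by arm and visit, including the between-arm difference in change.
3. Report with it the Helpful - misleading effect rescored on answered trials only. In simulation this removed all of a lapse artefact if every lapse was a time-out, about 40% if half were, and none if lapses were random guesses. It therefore complements item 2 and does not replace it.
4. Give the between-arm effect adjusted for change in no-context accuracy as a sensitivity analysis only, not as a go requirement. Agreement with the unadjusted effect is partial reassurance.

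The cost is a little more analysis of data already collected. No trial, visit or participant is added, and the go threshold is unchanged.
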